In conclusion, scientific research suggests that in the clinical setting, actigraphy is reliable for evaluating sleep patterns in patients with insomnia, for studying the effect of treatments designed to improve sleep, in the diagnosis of circadian rhythm disorders (including shift work), and in evaluating sleep in individuals who are less likely to tolerate PSG, such as inpatient psychiatric patients. While actigraphy has been used in research studies for many years, it is only recently that the methodological issues have been systematically addressed in clinical research and practice. With those issues addressed, the use of actigraphy is now being applied to clinical practice. (Ancoli-Israel et al, 2003).

STUDY OBJECTIVES

Primary Objective

To evaluate the effect of the Sleep Program on duration of admission in HDU (compared to controls) and sleep duration (Actigraphy data), in male psychiatric HDU inpatient participants.

Secondary objectives

1. Sleep quality - improvement in the Pittsburgh Sleep Quality Index
2. Sleep efficiency- percentage time in bed vs percentage time asleep
3. To test the engagement (tolerability and practicality) with a structured Stimulus Control Therapy Program
4. Impact on use of as needed (PRN) hypnotics
5. To describe the characteristic of sleep, activity and light exposure of patients in a high dependency psychiatric unit using wrist actigraphy.

Hypotheses

- We hypothesise that a structured stimulus control program for sleep will shorten duration of admission at psychiatric HDU.
- There will be an improvement in the sleep duration and efficiency
- There will be an improvement in the quality of sleep via a reduction of the self-rated Pittsburgh Sleep Quality Index score, measured at the beginning and end of the study.
- Participants in the Bright Light Study will engage in a structured stimulus control therapy program and it will be well-tolerated.

STUDY DESIGN

Design, Study Groups, Number of Participants

This is a pilot study for a complex intervention and we do not know the effect of variance. We seek to test our methodology, exterminate recruitment and retention rates, feasibility and finally, determine the sample size. We also seek to highlight any issues with acceptability, compliance, and delivery of our interventions.

Number of centres

Single-centre, at [name] Centre, male High Dependency (psychiatric) Unit

Duration

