We foresee the duration of the pilot study of approximately 6 months. Recruitment is on a continuous basis; with approximately 4-6 patients recruited at any given time.

Initial recruitment phase is one week, where patients are identified (see recruitment procedures).

Initial recruitment will be 4-6 patients. The patient is recruited for as long as they are an inpatient at the HDU and discontinued at their discharge (or at their request). Subsequent patients are then recruited in the same process to maintain 4-6 patients at any given time in the program for the duration of the pilot study.

PARTICIPANTS

Inclusion Criteria

1. Males 18+ years.
2. Inpatient in psychiatric Male HDU at PMBC
3. Willingness to give informed written consent and willingness to participate to and comply with the study.
4. Literacy in English.

Exclusion Criteria

1. Current substance dependence.
2. Severe cognitive impairment or thought disorder that does not allow participants to consent or follow treatment instructions.
3. Recent time-zone travel (within last 1 month).

STUDY OUTLINE

Interventions

The intervention is an integrated Sleep Program. It comprises of two main components, thrice weekly group sessions and ward environmental initiatives. The overarching aim is to improve sleep through;

1. **Increase daytime activity**, particularly in the morning if possible, with use of the balcony and outdoor areas. It has the ultimate aim of establishing routine. Many patients in a hospital setting experience a lack of activity. For example, patients may spend a lot of time in bed watching TV or napping throughout the day.
2. **Setting regular rhythms** – enhanced light/dark exposure to stabilize circadian rhythms.
3. **Stimulus control and relaxation** – simple breathing techniques, relaxing music through headphones, relaxation on bean bags
4. Encourage patient-driven management through **psychoeducation**, ongoing sleep quality monitoring and feedback, and driving behavioural change in the ward milieu.

The total duration of a patient’s participation in the Program is flexible. However, we consider a 2-week duration as the minimum dose.

Ward environmental initiatives

A number of initiatives are adopted, these are summarised below. They are specific to the participants of the study. Bean bag and visual cues (ward posters) are made available to the participants in their own rooms; while headphones are pre-existing equipment available to all patients in the HDU.

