	Friday PM 9 - 9:30pm	
 • Booster session • Wind down with beanbags • Headphones provided for relaxing music • Reinforcing stimulus control therapy 	X	X

Participant Time Line

Time Frame for Activity	Screen	Program cycle		
		At recruitment	Weekly	At discharge
Initial screening in handovers by clinical staff	X			
Initial medical assessment for appropriateness	X			
Self-report measures		X	x	X
Sleep Diary			X	
Qualitative evaluation Questionnaire				X
Ward initiatives		X	X	
Retimer™ Light goggles			X	
Actigraphy data		X	X	
Sleep Program groups		x	X	
Psychoeducation about sleep hygiene		X	X	
Program usage		X	X	X
Adverse event monitoring		X	X	X

Study Procedure Risks

1. Skin damage due to photosensitivity
Some medications, notably Chlorpromazine, are known to increase the photosensitivity of the skin. The Program entails exposure to natural and low intensity artificial light, which may cause irritation and minor sunburns.
2. Headache from tightness or poor fit of light spectacles
The Retimer™ light goggle is made from rigid plastic and are not adjustable for size of head. Therefore, it is possible that participants may experience discomfort on the ridge of their nose, or sections of the skin around the auricle which makes contact with the goggle.
3. Discomfort from artificial light
The Retimer light goggle emits light in two different intensity settings, which is projected upwards towards the light. Whilst the light intensity is safe, it may still be a source of discomfort and annoyance to the patient.
4. Sleep disturbance
The Program is an evidence-based intervention aimed to reset and align the circadian rhythm to normal daylight hours. However, there is a risk that the integrated intervention does not improve sleep quality and quantity, or indeed, may worsen them.
5. Psychological harm: wearing a watch which constantly collects data might further enhance persecutory or paranoid ideations in the sub-population of participants who are experiencing psychotic symptoms. However, given the study requires informed consent, the likelihood of a paranoid patient consenting to participate is small.

Given the non-invasive, interactive and patient-driven nature of the intervention, it is expected that participants will have minimal risks in the following domains:

- disclosure of sensitive personal information
- exposure of illegal activity
- economic harm
- discrimination, stigma or other social harm
- devaluation or harassment

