- 2) A factor found on examination of the device (a deterioration in characteristics or performance)

De-identified Serious Adverse Event Reports will be completed as required throughout the study period and sent the ethic committee.

Early Termination

Possible circumstances for early termination of the study include:

1. Early termination initiated by patient due to side-effects, change-of-mind, intolerability, or the perception that their sleep have improved sufficiently such that they no longer require participation in the program.
2. Loss of capacity to consent due to deterioration or variation in mental state
3. Loss of ability to participate due to deterioration or variation in mental state
4. Medical admission of patient due to an acute medical illness whilst inpatient at PMBC
5. Transfer of patient to a different facility.

The study coordinator will be responsible for correspondence with HREC.

Investigators involved in implementing the Sleep Program clinically, can receive formal notification of termination from the participant by verbal or written form. They may receive notice of termination through a delegate (such as the participant's nurse or medical officer responsible). The investigator will need to formally inform the Study Coordinator in written form.

The Study Coordinator will then be required to document termination in digital study data for this participant – whose data will be separated from overall data pool. Early termination data will be kept for discussion purposes but will be excluded in results and statistical analyses.

The Study Coordinator will be responsible for informing the

(who is responsible for what aspect in the process of terminating the study (informing participants, correspondence to HREC, compiling a final study report, unbinding if applicable)).

BLINDING AND UNBLINDING

- a) Blinding (Masking): This trial is an open-label with no attempt at masking
- b) Emergency unblinding: not applicable

STATISTICAL CONSIDERATIONS

Sample Size or Power Calculation

The pilot study will determine the sample size. Power calculation will be the minimum number of samples required to provide adequate power for the primary outcome. (Actigraphic changes in sleep duration)

Statistical Analysis Plan

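### The evaluation questionnaire is scheduled only at discharge, so men who stop the programme earlier have no scheduled evaluation and the questionnaire results would describe only those who stayed

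*Protocol*

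**What the plan says.** In the Participant Time Line the row reads "Qualitative evaluation Questionnaire X", and the one mark falls in the discharge column. There is none at recruitment or weekly.

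The Duration section names two ends to participation: "The patient is recruited for as long as they are an inpatient at the HDU and discontinued at their discharge (or at their request").

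The Early Termination section opens its list of reasons with "Early termination initiated by patient due to side-effects, change-of-mind, intolerability". The same sentence goes on to include men who feel they have slept well enough to need no more of the programme. The procedure that follows is notice (verbal or written, possibly through a delegate), a written report to the study coordinator, and documentation of the termination. No questionnaire or exit interview is mentioned. On the data, it says: "Early termination data will be kept for discussion purposes but will be excluded in results and statistical analyses".

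The Study Design section gives as one purpose of the pilot: "We also seek to highlight any issues with acceptability, compliance, and delivery of our interventions". The Administrative Information table lists autonomy and participant satisfaction among the key secondary outcomes.

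**The concern.** A pilot that sets out to find acceptability problems needs the views of men who stop as well as those of men who stay. Under the schedule as written, a man who stops at his own request and remains on the ward reaches no point at which the evaluation form is due. When he is eventually discharged from HDU he is no longer a participant.

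This is a gap in data collection, distinct from the rule that excludes early-termination data from the analysis. Lifting that rule alone would not bring back evaluations that were never sought. At stake is how far the questionnaire results can inform the design of the next study: they would speak for men who stayed to discharge, not for all who enrolled.

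**Working it through.** The protocol states no sample size, withdrawal rate or expected rating, so there is no figure to reproduce. The check sets the sections side by side.

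1. **When is the form due?** At discharge only (Participant Time Line).
2. **What does discharge mean?** The Duration section ties it to inpatient stay in HDU and contrasts it with stopping on request. The Informed Consent Process section also speaks of an expected discharge date from the HDU. The natural reading is HDU discharge, not programme exit.
3. **What happens when a man stops on request?** Notice and documentation (Early Termination). No form is triggered.
4. **Does anything else fill the gap?** In part:
   - Programme usage is recorded throughout ("Program usage X X X"), but it shows that a man stopped, not why.
   - Adverse events are followed throughout ("Adverse event monitoring X X X"), with open-ended questions. The circumstances must be documented when treatment stops because of an adverse event. A change of mind, or intolerability without an adverse event, falls outside that requirement.
   - Monday feedback concerns sleep. Friday feedback is an informal exchange.
   - The Patient Autonomy and Satisfaction Survey is not named in the time line. It may be the questionnaire in this row, or it may fall under the self-report measures, which are marked at recruitment, weekly and at discharge. The Physical Data section does not list it among the self-assessment forms, which favours the first reading without settling it.
5. **Which way would the selection push the results?** For any rating, write d for the share who stop early, and m_stay and m_leave for the mean ratings of the two groups. The mean among stayers exceeds the mean among all enrolled by

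   d × (m_stay − m_leave).

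   None of the three quantities is in the protocol. Purely as an assumption, take a 7-point scale, m_stay = 6 and d = 25%:
   - All who stop rate 4: the full mean is 0.75 × 6 + 0.25 × 4 = 5.5, so 6 overstates it by 0.5.
   - Half rate 4 and half, feeling better, rate 6: m_leave = 5, the full mean is 0.75 × 6 + 0.25 × 5 = 5.75, and the overstatement is 0.25.
   - All who stop feel better and rate 7: the full mean is 0.75 × 6 + 0.25 × 7 = 6.25, and 6 understates it by 0.25.

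   The sign depends on why men stop, and the protocol itself lists reasons of both kinds. These figures show only that dependence. They do not estimate the bias in this trial.

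**The case against.** The case against has real force on several points.

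- **The protocol is silent; it does not forbid asking.** The discharge column sits under a heading about the programme cycle, and the Session 2 text and sessions table tie the sleep quality index to the final week or terminating session. Discharge might therefore have been meant as programme exit. This stands as a possible reading. But the Duration section separates the two events, and staff following the time line have no trigger for a man who stops and remains on the ward. If exit was intended, the same edit makes it explicit.
- **Other acceptability data exist.** This stands. A reader might infer that acceptability as a whole is measured only in those who stayed. The documents do not support that: usage, adverse events and informal feedback are gathered from every participant until he stops.
- **The bias need not be upward.** This also stands. A reader might infer that satisfaction is bound to be overstated, because the missing men are the dissatisfied ones. The Early Termination list includes men who leave because they sleep better, so the direction is not fixed.
- **The survey could not show which components drove men out.** Correct. The appended survey asks about the relationship with practitioners. It has no items on goggles, groups or beanbags, so its ratings do not support the inference that the next trial would keep components that men disliked.
- **An exit form alone would change no reported result.** Correct, because of the exclusion rule. The fix must address both rules.

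**Conclusion.** The point holds in a limited form. The evaluation questionnaire has no scheduled administration for men who stop before discharge, and its results would describe only those who stayed. This rests on reading discharge as HDU discharge, which the Duration and Informed Consent Process sections support. Applying it to the autonomy and satisfaction survey as well requires the further assumption that the survey is given at the same point, which the protocol does not state.

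No size or direction can be attached to the selection bias. The gap concerns one form in an uncontrolled pilot and does not touch the actigraphic primary outcome. It is still worth closing before enrolment, because acceptability is one of the reasons for running the pilot and an evaluation not sought at exit may not be recoverable later.

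**What to change.** Make two linked changes.

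1. In the Participant Time Line, set the timing of the evaluation questionnaire to discharge or the point at which participation stops, whichever is first. Do the same for the autonomy and satisfaction survey if it is given at that point, and state its timing either way. At early exit the form should be optional, and offered only to men who have capacity and agree.
2. In Early Termination, amend the exclusion so that these ratings and the reasons for stopping are reported descriptively, separately from those of men who stayed to discharge. Without this, the new data would be collected and then left out of the report.

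The cost is two short text edits, a few extra forms and some effort at the time of exit. Some men who stop will decline, so the number offered the form and the number who completed it should be reported beside the ratings.

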Health
Sydney
Local Health District

PMBC Sleep Program

PROTOCOL NUMBER: VERSION 1.0 (APRIL 2018)

ADMINISTRATIVE INFORMATION

DATA CATEGORY	INFORMATION
Scientific Title	A pilot evaluation of sleep program to improve sleep quality in male psychiatric HDU inpatients
Public Title	PMBC sleep program
Date of Registration	TBC
Primary registry and trial identification number	TBC
Date of Registration in primary registry	TBC
Secondary identification numbers	TBC
Source of monetary or material support	Fully funded by the Sydney Local Health District (\$50,000)
Primary Sponsor	Sydney Local Health District
Contact for public queries	[name] [name], [contact]
Contact for scientific queries	[name] [name], [contact]
Countries of recruitment	Australia
Health condition(s) or problem(s) studied	Inpatient male HDU psychiatric patients of all diagnoses
Intervention(s)	Ward-based initiatives and activity groups
Comparator	Routine male inpatient psychiatric HDU patients' length of stay with and without therapy; previous admissions
Inclusion criteria	Males aged 18+ years. Able to give informed written consent. Literacy in English. Inpatient at PMBC psychiatric Male High Dependency Unit (HDU).
Exclusion criteria	Current substance dependence. Severely unwell such that not able to give consent or tolerating participation in group sessions. Severe cognitive impairment or thought disorder. Not

	proficient in English. Recent transmeridian (>2 time zones) travel (within last 1 month).
Study type	Interventional; Allocation: nonrandomized; Masking: none (open label trial)
Primary Purpose	Pilot Study, Feasibility Study
Date of first enrolment	May 2018
Target sample size	N/A (Pilot study, rolling recruitment)
Recruitment status	Recruitment not yet commenced.
Primary outcomes	Actigraphic changes in sleep duration (Respironics Actigraphy data)
Key secondary outcomes	
Sleep quality (weekly Visual Analogue Scale (VAS) and Pittsburgh Sleep Quality Index measured at start and end of study)
 
Self-report duration
 
Length of stay in HDU
 
Use of as needed (PRN) sedatives for sleep
 
Sleep efficiency (actigraphy)
 
Engagement in group
 
Autonomy
 
Participant satisfaction

Protocol Version:	Version 1.0, April 2018
Revision Chronology	Version 1.0, April 2018: Original.
Protocol Amendment Number	0
Authors	[name] BE(Hons) BCom MBBS, [name] BPsych(Hons), [name] MBBS PhD

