- familial distress
- harm to any member of a vulnerable population
- reputational harm

Informed Consent Process

There is a one-stage consent process to entry into the study. The Senior occupational therapist, [name] (investigator in this study) will introduce the study and discuss the main aspects to potential eligible participants in person in the first instance to reduce medical-patient power imbalance.

Participants will receive the study information sheets in hard copy. Research clinicians will discuss the study with participants in light of the information provided to them. The research clinician will obtain written content from patients willing to participate.

A potential participant has one week to consider their participation; however, they may defer that decision up until two weeks prior to their expected discharge date from the HDU - given a meaningful study period is defined as a minimum of two weeks of participation.

Enrolment Procedure

The participant will be enrolled into the study after the informed consent process has been completed and the participant has met all inclusion criteria and none of the exclusion criteria.

Participants need to be inpatient at HDU North (male) in PMBC, Royal Prince Alfred Hospital.

Participants are first identified as potential (candidate) participant by medical/OT/SW/RN from Multi-Disciplinary Team (MDT) meeting, satisfying inclusion and exclusion criteria.

The participant will receive a study enrolment number (Participant ID number), and this will be documented in secure and confidential register, as well as in the medical records.

Capacity

Potential (candidate) participants are clinically assessed for the ability to understand and capacity to give consent. The consultant in the treating team must deem the candidate participant as having capacity to consent; and this must be a consensus impression by the rest of the MDT. Further, it must be verifiable by demonstrated understanding and engagement with the Sleep Program. Mental state is monitored on an ongoing basis as per standard care. In cases where a participant deteriorates or loses capacity to consent and participate altogether: their involvement in the study will cease. This is outlined under *Early Terminations*.

Randomisation Procedure

Not applicable

Adverse Event Reporting

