Given the pilot study nature we will describe the sample, and the outcomes using but only use analytical techniques to estimate potential effects using difference of means within person measures in SPSS. The pilot study is unlikely to generate sufficient data points for bivariate or multivariate regression modelling.

DATA SECURITY, STORAGE AND ARCHIVING OF STUDY DOCUMENTS

Data Safety and Storage

There are two forms of data collected in pilot study: digital data, and physical data handwritten on paper forms.

Digital Data

Patient name, MRN and date of birth are linked to a Participant ID number. This is kept on an Excel spreadsheet, which is password protected on a single desktop issued by the Sydney Local Health District. The computer will be kept on-site only, in the secured, staff-only section of PMBC, which is accessible via swipe card only. The patient data spreadsheet can only be accessible within a Sydney LHD premises which has access to the SLHD intranet. Back-up copy of this spreadsheet is kept within the Sydney LHD ICT infrastructure.

De-identified digital data includes all data that are entered digitally, and are only identifiable through Participant ID. This includes any digitised data from physical forms, actigraphy data, aggregate length-of-stay data, and so on. Computers with access to these files that are password-protected and individualised for the investigator.

For security, a complete back-up of the data will be kept on a separate, secure Sydney LHD laptop, and is performed on a daily basis. Periodic data analysis files will also be backed-up and kept. Primary access to the Sydney LHD computing facilities will be through physical access onsite and through the intranet. Security will be enforced through restricted, swipe-card physical access, passwords and different levels will be assigned to groups and individuals.

Physical Data

Physical data includes the following; patient-completed self-assessment forms (PSQI, sleep diary, Visual scales), equipment check-in and check-out equipment logs. These are identifiable to patient with *only* the Participant ID.

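### Participants are selected on expected remaining HDU stay and controls are not, so the planned length-of-stay comparison is biased towards a longer stay in participants

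*Protocol*

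**What the plan says.** The Protocol's Informed Consent Process section gives a candidate a week to think: "A potential participant has one week to consider their participation". The decision can be put off for longer, but "they may defer that decision up until two weeks prior to their expected discharge date from the HDU", the reason being "given a meaningful study period is defined as a minimum of two weeks of participation". The Interventions section agrees: participation is flexible in length, but "we consider a 2-week duration as the minimum dose".

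The Primary Objective is to evaluate the "effect of the Sleep Program on duration of admission in HDU (compared to controls"), together with actigraphic sleep duration. The first hypothesis is a shorter HDU admission. The Administrative Information table lists length of stay only as a key secondary outcome and gives the comparator as "Routine male inpatient psychiatric HDU patients' length of stay with and without therapy; previous admissions". No minimum stay, matched day of stay or start of the clock is set for any comparator.

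The Early Termination section removes early terminators from results and analyses. They include patients who leave because their sleep has improved enough and patients transferred elsewhere. The Statistical Analysis Plan section mentions only within-person differences of means. The Digital Data section includes "aggregate length-of-stay data" among the de-identified data held.

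**The concern.** The consent window depends on a forecast of the quantity that is later compared. A patient expected to leave the HDU soon falls outside the window; one expected to stay long falls inside it. Nothing stated for routine patients or previous admissions removes their short stays. Participants must also still be in the HDU on the day they enter, so the days before entry count towards their total stay but cannot reflect the programme.

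The first hypothesis is at stake. The selection pushes against it: a programme with no effect could appear to lengthen stay, and one that shortens stay could appear neutral or harmful. The pilot is meant to determine the effect and its variance for later planning, so a distorted length-of-stay estimate would carry forward.

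**Working it through.** **Nothing to reproduce.** The Protocol states no mean HDU stay, spread, usual entry day or target sample size. The calculation below shows the direction of the bias and how its size depends on assumptions.

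**Inputs from the Protocol**
- Expected remaining stay at the latest decision point: 14 days (Informed Consent Process).
- Comparators: routine HDU stays and previous admissions, with no matching rule (Administrative Information).
- Only length-of-stay effect cited: 3.67 days, for east- against west-facing rooms (Background). It is a yardstick, not a design effect.

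**Assumptions**
- Entry day *e* is uniform on day 0 to 7, guided by the one-week consideration period.
- Mean total stay *m* is 14, 21 or 28 days.
- There is no programme effect, and participants and controls come from the same stay distribution.
- The 14-day rule is first applied to actual stay, then to an imperfect forecast.

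**Formula.** With *T* the total HDU stay, bias = E[*T* | *T* ≥ *e* + 14] − E[*T*].

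For exponential stays, E[*T* | *T* ≥ *e* + 14] = *m* + 14 + *e*, so the bias is 14 + *e* at any mean: +14 for entry on day 0, +17 on day 3, +21 on day 7.

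**Simulation, entry spread over day 0-7.** Participants' mean total stay, with the bias against *m* in brackets:

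| Shape of stay distribution | *m* = 14 | *m* = 21 | *m* = 28 |
|---|---|---|---|
| Exponential | 31.3 (+17.3) | 38.3 (+17.3) | 45.4 (+17.4) |
| Log-normal, CV 0.8 | 28.1 (+14.1) | 32.8 (+11.8) | 37.8 (+9.8) |
| Gamma, shape 4 | 22.8 (+8.8) | 27.6 (+6.6) | 32.9 (+4.9) |

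**Imperfect forecast.** The rule uses the expected discharge date. With a log-normal forecast error (log-SD 0.4), participants' means at *m* = 14, 21 and 28 are:
- exponential: 30.2, 37.9 and 45.3, so the bias is +16.2, +16.9 and +17.3;
- log-normal: 26.2, 32.0 and 37.6, so the bias is +12.2, +11.0 and +9.6.

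Forecast error reduces the bias somewhat but does not remove it.

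**Wider grid.** With means of 7 to 60 days, CV 0.5 to 1.2 and fixed entry on day 0, 3 or 7, the bias runs from about +0.1 to +27 days. It is positive throughout and exceeds 3.67 days in most scenarios, but not all: gamma shape 4 with mean 28 and entry on day 0 gives +2.9.

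**Choice of clock.** The Protocol does not say whether stay runs from admission or from entry. If participants were counted from entry and controls from admission, the difference could be smaller, or slightly negative where stays are long and not very variable. If controls are given a matched entry day but no two-week rule, and both groups are counted from entry, about +5 to +14 days remains in the table's scenarios. Both conditions have to be matched.

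**After matching.** If controls are still in the HDU on the matched day, meet the same expected-remaining-stay rule and are counted from that day, both groups estimate the same conditional mean. The selection difference under no effect is then 0.

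**The case against.** The strongest reply is that the sentence limits how long consent may be deferred. It is not a listed inclusion criterion, it refers to an expected date, and participation ends at discharge or on request. A reader might infer a guaranteed two-week stay, in effect immortal time. The documents do not support that: discharge before day 14 is possible and is not listed as an early termination. In imperfect-forecast scenarios (means 10-42 days, log-SD 0.3 to 1.0) between 2% and 71% of entrants leave before completing two weeks. What remains is selection on expected stay, which still biases the comparison.

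Other points stand in part:
- A reader might take +10 to +17 days as the bias, or call it 3 to 5 times the cited 3.67 days. Those figures belong to the exponential and log-normal rows only. The Protocol supplies nothing that fixes them, and 3.67 days concerns room orientation.
- The calculation draws both groups from one population. Participants must also have capacity and no substance dependence, and no such screen is stated for routine controls. This may shift the net difference in an unknown direction, so it cannot be said that participants will certainly appear to stay longer.
- Previous admissions are a within-person comparator and were not modelled. The size there depends on within-person correlation.
- It is tempting to conclude that control stays cannot be restricted because the data are aggregate. That phrase is an example in a storage paragraph and does not show that per-admission data are unavailable.
- This is a pilot with descriptive aims, sample size is tied to actigraphic sleep duration, and the bias is unlikely to create a false benefit. That limits the harm, but length of stay is in the primary objective and leads the hypotheses.
- A separate SAP, not shown, could define the start of the clock. The entry rule and the comparator are nevertheless fixed in this Protocol, and forecasts not recorded at the time cannot be used later.

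**Conclusion.** The concern holds as a selection bias. Entry depends on expected remaining HDU stay, the comparators face no equivalent rule, and early terminators are excluded from participants only. With no effect and otherwise similar patients, participants' total stay is biased upwards, against the first hypothesis.

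The size is an assumption, not a finding from the documents: about +5 to +17 days for entry on day 0-7 and mean stays of 14-28 days (exponential about +17, log-normal CV 0.8 about +10 to +14, gamma shape 4 about +5 to +9), and from near 0 to over 25 days on the wider grid. The net difference also depends on the other entry criteria, whose effect on stay is unknown. As written, the control comparison cannot be read as an effect of the programme on HDU stay.

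**What to change.** 1. Define time zero as the day of entry and compare remaining HDU stay from that day.
2. Use per-admission de-identified stay data for controls. Include only admissions still in the HDU on the matched day of stay that meet the same expected-remaining-stay rule, where forecasts are recorded. Record the expected discharge date at entry for participants.
3. Where control forecasts are not recorded, use a landmark at entry + 14 days in both groups and label the result conditional on reaching it. This misses discharges in the first 14 days, which the programme might itself change, and leaves roughly 1 to 3 days of bias when forecasts are imperfect.
4. Keep early terminators in the length-of-stay analysis, within the terms of their consent.
5. If none of this is feasible, report participants' stay descriptively with no control comparison.
6. Reconcile the Administrative Information table with the Primary Objective on whether length of stay is primary or secondary.

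The cost is Protocol wording, one extra recorded date per participant and a per-admission extract. Recruitment is stated not to have begun, so the forecast date can still be collected from the first participant.
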